## **6.0 Procedures Involved\***

6.1-6.4 The objective is to develop and pilot a novel streamlined approach to deliver genetic education and testing to the rapidly increasing number of prostate cancer patients who meet guidelines for genetic referral. Our streamlined genetic testing approach is designed to facilitate genetic education and testing for men with prostate cancer. The intervention will incorporate proactively delivered print educational materials in lieu of pre-test genetic counseling. The materials will increase awareness, expand access, provide

balanced information to foster informed genetic testing decisions and reduce barriers to facilitate the delivery of genetic testing. All men who are found to carry a PV or variant of uncertain significance (VUS) in a cancer risk gene will have an individual telephone genetic counseling disclosure session with a board-certified genetic counselor. We will recruit 120 prostate cancer survivors who meet clinical referral criteria. After a baseline survey, we will randomize participants to: ST vs. UC. Participants will complete a follow-up survey at 2-3-months post-randomization. Our primary outcome is genetic testing uptake.

Eligibility and Accrual. Men eligible for this study are currently being followed at MGUH or MWHC for either:

Metastatic prostate cancer;  
Gleason 7+ prostate cancer.

We will exclude patients who have had, or are already scheduled for genetic counseling or testing for *BRCA1* or *BRCA2* mutations. We will also exclude men who cannot participate in English and provide meaningful consent. We will recruit participants from medical and radiation oncology clinics at MGUH and MWHC. These clinics currently follow well over 1000 eligible patients.

Gender and Minorities. Participants will be adult men. Given the racial/ethnic breakdown of the clinics we are recruiting from. We expect that at least 30% of participants will be members of racial/ethnic minority groups.

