Recruitment. Working with our clinical collaborators and the Survey, Recruitment and Biospecimen Collection Shared Resource (SRBSR) will obtain contact information of potentially eligible patients from clinical databases and/or the EMR. We will mail an introductory letter describing the study (from the study MPIs and the patient's physician), opt-out postcard/phone number, informed consent document and a print version of the baseline survey to all potentially eligible participants. We will also email electronic versions of these materials for patients who prefer to complete them online. Two-weeks following this mailing, an SRBSR research assistant (RA) will call patients who have neither opted out nor completed the baseline survey. For men who have not returned the consent document, we will use an IRB-approved verbal consent for completing the baseline survey and request return of the written consent prior to randomization. Following completion of print or electronic consent and the baseline survey, the RA will randomize participants. Men randomized to ST will be sent a priority mail packet with detailed genetic testing educational material. Men randomized to UC will be mailed a letter informing them that they meet guidelines for genetic counseling and provided with contact information to schedule a genetic counseling appointment with a LCCC genetic counselor.

Randomization. Following completion of the baseline survey and consent document, an RA will randomize participants via computer-generated random numbers in blocks of 8 and a ratio of 1:1. Participants will be notified of their random assignment via letter and email.

**Assessments.** We will administer baseline (T0) and 2- to 3-month (T1) follow-up telephone/electronic surveys. Genetic testing uptake will be assessed via clinical records and basic clinical and demographic information abstracted from the EMR. See Table 1 for assessment instruments and schedule of administration.

Table 1. Measures		T0	T1
Variables	Measures		
Covariates/Background Variables	Demographics, clinical variables, family history (EMR/survey)	X	
Health Literacy	Brief Health Literacy Screening Tool	X	
Genetic Test Uptake	Study Records		X
Knowledge/Risk Comprehension	Genetic Knowledge Scale and Perceived Mutation Risk.	X	X
Attitudes	Adapted version of the Multimodal Measure of Informed Choice (MMIC), Fatalism, Medical Mistrust Index	X	
Decision Regret	Decisional-Regret Scale.		X

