## **17.0 Data Management\* and Confidentiality**

*17.1* Data Analysis: We will characterize participants by comparing them to decliners on key demographic and clinical variables derived from the EMR. After performing univariate analysis on dependent variables, we will apply any needed normalizing or variance stabilizing transformations. We will follow Consort guidelines for Intent-to-Treat analyses (ITT). We will compare groups at baseline with  $\chi^2$  and t-tests and will include covariates that are associated with group ( $p < 0.10$ ) in our final models.

**Aim 1: Evaluate the impact of Proactive Streamlined Education and Testing (ST) vs. Usual Care (UC) on genetic testing.** Analysis: H1.1: Patients randomized to ST will be more likely to complete genetic testing compared to UC. We will use logistic regression to test this hypothesis. After entering significant covariates, we will add intervention arm to test the overall intervention effect. H1.2: Participants randomized to ST will make better informed genetic testing decisions (characterized by high knowledge, risk comprehension and positive attitudes) compared to UC. Using multiple regression, we will enter control/confounding variables and intervention to test the impact of group on our informed decision making outcomes (knowledge, testing attitudes, risk comprehension). H1.3: Few patients in the ST arm will opt for traditional genetic counseling prior to testing. We will conduct descriptive analyses describing the proportion of ST participants who opt for genetic counseling vs. proceed directly to testing vs. opt against testing.

**Aim 2: Evaluate patient satisfaction and psychosocial outcomes in ST vs. UC.** Analysis: H2.1: Compared to UC, those randomized to ST will be more satisfied with their genetic testing decision and will have less decisional regret. After identifying baseline confounders of each outcome, we will generate linear regression models in which we enter: 1) confounders; 2) genetic test result (dummy

coded to generate comparisons of carriers vs. non-carriers and non-carriers vs. untested); 3) group assignment. In the event that we have an insufficient number of PV carriers for these analyses, we will categorize test result into two levels (tested vs. untested) and evaluate results among PV carriers more descriptively. Results of Aim 2 analyses will be primarily focused on generating effect size estimates for our planned trial of newly diagnosed prostate cancer patients.

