**Aim 3: Evaluate the impact of ST vs. UC on uptake of cascade testing in unaffected family members.** In exploratory analyses designed to provide effect size estimates for our planned R01, we will use t-test to compare the ST to UC on the number of relatives of PV carriers who undergo cascade genetic testing.

**Power:** Power estimates are for 2-tailed tests ( $\alpha=.05$ ). The study is powered based on our primary outcome of patient genetic testing uptake. We expect no attrition since data will be abstracted from clinic records. With no relevant studies on which

Table 2. Sample Size Calculation			
	ST Uptake		
UC Uptake	.40	.45	.50
10%	39	25	20
15%	49	36	27
20%	81	54	39

to base our effect sizes for this pilot study, Table 2 displays the necessary sample size (per group) to obtain 80% power for a range of potential clinically significant effects on test uptake (40%-50% for ST; 10%-20% for UC). Based on this analysis, we will enroll 120 participants in order to attain 80% power to detect a clinically meaningful difference between 20% in UC and 45% in ST. For our secondary outcomes, a sample size of 120 and 10% attrition at 3-months (n=108 in final sample) will provide  $> 80\%$  power to detect medium sized effects of  $d=.54$  SDs on our secondary outcomes (e.g., decisional conflict, patient satisfaction). This effect size is well within the range that we have seen in previous studies and represents an effect that is generally considered to be clinically significant.

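### H1.2 does not pre-specify the T0 score as a covariate for T1 genetic knowledge and perceived mutation risk, although both are measured before randomization

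*Combined protocol and SAP*

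**What the plan says.** Section 17.1, Aim 1, describes the H1.2 analysis in one sentence: "Using multiple regression, we will enter control/confounding variables and intervention to test the impact of group on our informed decision making outcomes". The outcomes are listed there as "knowledge, testing attitudes, risk comprehension". The control or confounding variables are not listed.

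The opening paragraph of 17.1 gives a general rule: the arms are compared at baseline, and the final models "will include covariates that are associated with group" at p<0.10.

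In Table 1 (section 6.0), the knowledge and risk comprehension row, "Genetic Knowledge Scale and Perceived Mutation Risk", is marked at both T0 and T1. T0 precedes allocation: "Following completion of print or electronic consent and the baseline survey, the RA will randomize participants". T1 is the later survey: "Participants will complete a follow-up survey at 2-3-months post-randomization". The attitudes row, "Adapted version of the Multimodal Measure of Informed Choice (MMIC), Fatalism, Medical Mistrust Index", is marked at T0 only.

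The power paragraph of 17.1 allows for 10% attrition from 120 (108 analysed) and claims more than 80% power for d=0.54 on secondary outcomes.

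**The concern.** A baseline score on the same instrument is often the strongest available predictor of the follow-up score, and here it is a clean pre-randomization covariate already being collected. The plan neither commits to using it nor rules it out.

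The p<0.10 rule does not fill that gap, because it asks whether a variable differs between arms and not whether it predicts the outcome. Under randomization any baseline difference is due to chance, so a T0 score passes about one time in ten however prognostic it is.

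The rule also disturbs calibration. When T0 is left out because the arms look balanced on it, the unadjusted standard error still allows for T0 imbalance that the selection has largely excluded. That standard error is therefore too large, and the test rejects less often than 5% under the null.

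At stake is the width of the interval for the informed-decision comparison, in a pilot meant to give preliminary efficacy data for a larger trial. If adjustment is instead left to judgement, an analytic choice that can move the result is open after the data are seen.

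**Working it through.** **Inputs from the documents**
- 120 enrolled, 1:1, 10% attrition: 120 × 0.90 = 108, or n = 54 per arm (sections 6.0 and 17.1).
- d = 0.54 SD on the unadjusted scale, two-sided α = 0.05 (17.1: "Power estimates are for 2-tailed tests").
- Entry rule: baseline association with arm at p<0.10 (17.1).

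**Assumption.** The correlation ρ between T0 and T1 scores is not given. I use 0.3, 0.5 and 0.7.

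**1. Reproduce the plan's figure.** With no baseline adjustment, the standardized difference is d·√(n/2) = 0.54 × √27 = 2.806. Normal-approximation power is Φ(2.806 − 1.960) = Φ(0.846) = 80.1%; the noncentral t gives 79.4%. The detectable d at 80% power is 0.54. The stated figure therefore matches an unadjusted two-sample comparison.

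**2. T0 always in the model.** The residual SD is multiplied by √(1 − ρ²), so the standardized difference becomes 2.806/√(1 − ρ²), with 108 − 3 = 105 degrees of freedom. Effective sample size is 108/(1 − ρ²).

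| ρ | √(1 − ρ²) | Variance reduction (ρ²) | Power, normal | Power, t | Detectable d (t) | Effective N |
|---|---|---|---|---|---|---|
| none | 1 | 0 | 80.1% | 79.4% | 0.54 | 108 |
| 0.3 | 0.954 | 9% | 83.7% | 83.0% | 0.52 | 119 |
| 0.5 | 0.866 | 25% | 90.0% | 89.4% | 0.47 | 144 |
| 0.7 | 0.714 | 49% | 97.6% | 97.3% | 0.39 | 212 |

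**3. The p<0.10 rule, by simulation.** Bivariate normal T0 and T1 scores, 54 per arm. T0 enters only if its t-test between arms gives p<0.10.

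| ρ | T0 enters | Power at d=0.54, rule | Power at d=0.54, always adjusted | Actual size of 5% test, rule |
|---|---|---|---|---|
| 0.3 | about 10% | 80% | 83% | about 4.6% |
| 0.5 | about 10% | 81% | 89% | about 4% |
| 0.7 | about 10% | 83% | 97% | about 3% |

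Unadjusted power in the same simulations is 79 to 80%. Always adjusting keeps the size at about 5% throughout. Repeated runs agree to within a few tenths of a percentage point. The rule thus recovers only a small part of the available gain.

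**The case against.** The strongest reply is that the plan does not exclude the T0 score. The H1.2 wording is open-ended, and a baseline value of the outcome is an ordinary control variable. Nor is the p<0.10 sentence stated to be exclusive: elsewhere in 17.1, H1.1 refers to significant covariates and Aim 2 to baseline confounders of each outcome. This stands. A reader might infer that H1.2 will be fitted without T0, or that p<0.10 is the sole gate; the documents support neither. What remains is that inclusion is not specified. The 10% entry rate and the reduced test size apply only if the p<0.10 rule governs.

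A second reply is that the plan already reaches about 80% power at its own d=0.54 without adjustment. That also stands. The gain is extra precision, and its size rests on an assumed correlation. At ρ = 0.3 it is about three percentage points of power. It could be smaller still for perceived mutation risk, since some men may have their test result by T1, which could weaken the link with T0. At ρ = 0.1 the variance falls by only 0.1² = 1%.

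Two other readings are tempting. A reader might take H1.2 as the evidence that skipping pre-test counselling leaves men no less informed. However, sections 2.0 and 17.1 state it as superiority of ST, and no non-inferiority margin appears. A reader might also suspect bias or false positives. Randomization keeps the T1 comparison unbiased without T0, and the calibration error is in the conservative direction.

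**Conclusion.** The point holds as a gap in specification: 17.1 does not commit to adjusting T1 knowledge and T1 perceived mutation risk for their own T0 scores, and the one explicit rule that applies would usually leave them out.

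At the plan's n=108 and d=0.54, committing to the adjustment is worth about 3, 8 and 14 percentage points of power over the p<0.10 rule at ρ = 0.3, 0.5 and 0.7 (83 − 80, 89 − 81, 97 − 83). It also restores a 5% test. These figures assume normally distributed scores, a common ρ in both arms, and that the p<0.10 rule would otherwise decide entry. If the choice is discretionary, the cost is an unfixed analysis and not a calculable loss.

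The consequence is limited to the precision and calibration of a secondary hypothesis. Testing uptake, the primary outcome, is unaffected.

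**What to change.** In 17.1, under H1.2, state that T1 genetic knowledge and T1 perceived mutation risk are each analysed by ANCOVA with terms for arm and the T0 score of the same measure, and that the T0 score is always included whatever its baseline p-value. Any further covariates can follow the plan's existing wording.

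The cost is one sentence and one degree of freedom per model (106 to 105 with no other covariates). It needs no new data and no extra participants. Even at a correlation near zero, that degree of freedom is essentially the whole price.

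The sentence should not extend to attitudes. Table 1 schedules those at T0 only, so there is no T1 attitude score to adjust.

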## **4.0 Study Endpoints\***

### **4.1 Primary and secondary endpoints:**

1. Genetic test uptake
2. Receipt of pre-test genetic counseling
3. Psychosocial outcomes (Satisfaction, distress, decision regret)
4. Use of cascade testing among unaffected family members of mutation carriers

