Decision Satisfaction	Satisfaction with Decision Scale.		X
Distress	Cancer distress: PROMIS Anxiety and Depression; Genetic testing distress MICRA.	X	X
Quality of Life/Functional Status	PROMIS Physical Function and Social Function Short Forms	X	X
Cascade Testing	Number of relatives who have proceeded with genetic testing.		X

**Streamlined Testing (ST) Intervention.** Men randomized to ST will be sent a priority mail packet with the ST print education materials and information on how to proceed with genetic testing. ST participants will have the option of proceeding directly to genetic testing or scheduling a telephone genetic counseling session. The content of the ST intervention is described in section 5.0 above.

**Usual Care (UC).** After completion of the baseline survey, UC participants will be sent a letter from their physician indicating that they meet eligibility criteria for genetic testing, recommending that they schedule genetic counseling and providing a contact telephone number to schedule their session. Patients may opt for free telephone genetic counseling.

**Genetic Testing.** Participants who choose to pursue genetic testing will be offered a standard clinical multigene panel of at least 40 genes, including *BRCA* and genes associated with potential differential diagnoses (e.g., Lynch syndrome). All testing will be performed by Invitae, a CLIA certified clinical lab not affiliated with the GLCCC. Invitae offers genetic testing free of charge to eligible prostate cancer patients (all study participants will be eligible for free genetic testing through Invitae). Prior to proceeding with genetic testing, participants will be required to sign and return a clinical genetic testing consent form, after which we will mail them an at-home DNA kit for saliva collection which will be returned directly to Invitae (shipping costs are pre-paid).

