There may also be risks for ST participants who proceed directly to genetic testing without an individual genetic counseling session. However, we believe that the risk to these participants is low for several reasons. A) In community practice approximately 50% of individuals who receive cancer genetic testing do so without any pre-test genetic education or counseling; B) All participants who are randomized to ST will have the option to request individual telephone genetic counseling free of charge through the study; C) All individuals who proceed to genetic testing and are found to carry a PV or VUS result will receive their test results in the context of a standard genetic counseling disclosure session with a board-certified genetic counselor; D) The population in the current study all meet guidelines for genetic referral. There are insufficient counseling resources to retrospectively contact and counsel all prostate cancer survivors who meet criteria for genetic testing. Thus, from a clinical perspective, it is critical to develop effective and efficient genetic education approaches to foster informed genetic testing decisions. Finally, the personal health implications of a positive genetic test result in men are much less pronounced and immediate than in women. Thus, the risk of adverse psychosocial outcomes (already low in women who undergo testing) is quite low.

For all patients who choose to proceed with genetic testing, there may be additional risks. Although participants will neither be encouraged nor discouraged from undergoing testing as part of this study, for those who choose to pursue testing, additional potential risks include insurance and employment discrimination and the small possibility of incorrect or inaccurate test results. The ST materials contain information about laws protecting against genetic discrimination, and the standard clinical laboratory consent form outlines the small possibility of incorrect or inaccurate test results.

Finally, in addition to psychosocial risks that may be associated with genetic counseling, there may also be risks related to confidentiality and loss of privacy should an unauthorized third-party learn that the participant received genetic counseling and testing.

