## **18.0 Provisions to Monitor the Data to Ensure the Safety of Subjects\***

This research does not involve more than minimal risk to subjects.

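### Distress is a listed endpoint measured at T0 and T1, but Aim 2 names no analysis for it, and the generic Aim 2 model would not estimate the total effect of ST on distress

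*Combined protocol and SAP*

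**What the plan says.** Section 4.1 includes among the endpoints "Psychosocial outcomes (Satisfaction, distress, decision regret". The Distress row of Table 1 (section 6.0) gives the instruments, "Cancer distress: PROMIS Anxiety and Depression; Genetic testing distress MICRA", and marks them at both T0 and T1. Decision regret and decision satisfaction are marked at T1 only.

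In section 17.1, Aim 2 is headed "Evaluate patient satisfaction and psychosocial outcomes in ST vs. UC". Its single hypothesis, H2.1, is that "those randomized to ST will be more satisfied with their genetic testing decision and will have less decisional regret". The analysis is then described once, for outcomes that are not listed: "After identifying baseline confounders of each outcome, we will generate linear regression models in which we enter: 1) confounders; 2) genetic test result". Group assignment enters third. Test result is dummy coded as carrier against non-carrier and non-carrier against untested. If carriers are too few, it falls back to tested against untested.

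Section 17.1 does not name distress. It gives no direction, lead scale, baseline adjustment, analysis set or margin for it, and the power paragraph's examples of secondary outcomes leave it out.

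**The concern.** Distress is the one listed psychosocial endpoint with a baseline measurement, and it bears most directly on possible harm. Section 15.1 concedes: "There may also be risks for ST participants who proceed directly to genetic testing without an individual genetic counseling session". It then argues that this risk is low and judges adverse psychosocial outcomes unlikely. No analysis is explicitly planned that would put a number on that judgement, although randomised data are collected at both time points.

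Two things are at stake. If distress is left out of Aim 2, or analysed only after the results are seen, the trial can report uptake, satisfaction and regret without a prespecified estimate on the outcome most likely to count against ST. If distress is put through the Aim 2 model as written, the reported group coefficient answers a different question from whether offering ST changes distress. Either result would carry into the effect sizes intended for the next trial.

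**Working it through.** **1. Where distress appears**

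| Place | Distress |
|---|---|
| Section 4.1 | Listed with satisfaction and decision regret |
| Table 1 | PROMIS Anxiety and Depression, and MICRA, at T0 and T1 |
| H2.1 (sections 2.0 and 17.1) | Not named |
| Aim 2 model (17.1) | Covered only if the unlisted outcomes include it |
| Power paragraph (17.1) | Not among the examples |

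**2. The plan's own figure.** The power paragraph gives 120 enrolled and 10% attrition, so 120 × 0.9 = 108, or 54 per arm, with two-sided alpha 0.05 and d = 0.54. The standard error of the arm difference in SD units is √(2/54) = 0.1925. Power = Φ(0.54/0.1925 − 1.96) = Φ(0.85) = 80.1%; the exact t-test gives 79.4%. The stated figure of just over 80% is reproduced under the normal approximation.

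**3. What the generic model would estimate.** Both codings of test result contain a tested/untested contrast. Under the uptake used to size the trial, 45% of ST men and 20% of UC men are tested, a difference of 25 percentage points. If being tested shifts T1 distress by δ SD on average, testing contributes 0.25 × δ to the total ST−UC difference. Entering test result removes that path from the group coefficient. The sign of δ is unknown, so the adjustment could hide a rise or a fall. Men who choose testing may also differ from those who do not, and differently in each arm, so conditioning on testing weakens the protection of randomisation.

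T0 distress enters only if it is associated with arm at p<0.10 (the general rule in 17.1) or is identified as a baseline confounder (the Aim 2 rule). Neither guarantees it.

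**4. Precision of a direct comparison.** Half-width = t(0.975) × √(2/n) × √(1 − r²), where r is the T0–T1 correlation. The documents give no r, so a range is assumed. Degrees of freedom are 106 unadjusted and 105 adjusted; t is 1.98 in both cases.

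| | n = 54 per arm | n = 51 per arm |
|---|---|---|
| Unadjusted | 0.38 SD | 0.39 SD |
| r = 0.5 | 0.33 | 0.34 |
| r = 0.6 | 0.31 | 0.31 |
| r = 0.7 | 0.27 | 0.28 |

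The second column uses the roughly 15% withdrawal quoted in section 14.3: 120 × 0.85 = 102, or 51 per arm.

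**5. What could be excluded.** If the true difference is zero, the chance that the upper 95% limit falls below a rise of m SD is Φ(m/(0.1925 × √(1 − r²)) − 1.96). The values of m are assumptions; the documents state no margin.

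| m (SD) | Unadjusted | r = 0.5 | r = 0.7 |
|---|---|---|---|
| 0.2 | 18% | 22% | 31% |
| 0.3 | 34% | 44% | 59% |
| 0.4 | 55% | 67% | 83% |
| 0.5 | 74% | 85% | 95% |

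The same formula gives the power to detect a true rise of m. A real rise of 0.3 SD would be non-significant about two times in three without adjustment (100% − 34% = 66%).

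**6. MICRA.** Table 1 labels it as genetic testing distress and does not say who completes it. If it applies only to tested men, the planning uptake gives about 0.45 × 54 = 24 ST men and 0.20 × 54 = 11 UC men, with a half-width of 1.96 × √(1/24.3 + 1/10.8) = 0.72 SD. Those groups would be selected after randomisation, so a descriptive summary suits MICRA better than an arm test.

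**The case against.** The strongest reply is that distress is already covered. The Aim 2 heading refers to psychosocial outcomes, section 4.1 defines these to include distress, and the model is written for every outcome. A comparison needs no directional hypothesis, and the plan says that "Results of Aim 2 analyses will be primarily focused on generating effect size estimates for our planned trial". This part stands: the documents do not support the reading that no model compares distress between arms, or that the trial cannot say whether ST raises it. Scores are due in both arms at both times, so an estimate is obtainable. But this reply leads to the model in step 3, which does not give the total effect.

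A reader might also infer that distress is documented as the main harm of bypassing counselling. It is not. Section 15.1 links mild distress to genetic education or counselling generally; for direct testing it speaks of unspecified risks and then of adverse psychosocial outcomes.

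Nor is distress unmonitored. Section 18.0 says only "This research does not involve more than minimal risk to subjects", but section 15.1 refers participants who report high distress for psychological assessment and has counsellors assess it at disclosure of PV and VUS results. What is missing is a comparison between arms.

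Finally, an all-randomised comparison dilutes any harm confined to tested ST men. At 45% uptake, an arm-level limit of 0.27 to 0.38 SD is compatible with 0.27/0.45 = 0.60 to 0.38/0.45 = 0.84 SD among them. That is a fair limit on what the comparison can show, but it remains the only contrast protected by randomisation.

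**Conclusion.** The point holds as a gap in specification with a real estimation problem behind it. Distress has no named analysis. The only model that could be taken to cover it conditions on a post-randomisation variable with an expected 25-point difference between arms, and it leaves baseline adjustment to chance.

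A prespecified comparison would give an ST−UC estimate with a half-width of about 0.38 SD unadjusted, or 0.33 to 0.27 SD with the T0 score. This assumes 54 men per arm with T1 data and a T0–T1 correlation of 0.5 to 0.7.

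It is tempting to conclude that these data would rule out a moderate increase. That is likely only with T0 adjustment (85% to 95% for an assumed 0.5 SD when there is no true difference) and is not assured. A rise of 0.2 to 0.3 SD cannot be reliably excluded in any of these scenarios.

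**What to change.** Add to Aim 2 in section 17.1:

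- Distress will be compared in all randomised men with T1 data, tested or not, analysed as randomised.
- T1 PROMIS Anxiety and T1 PROMIS Depression will each be regressed on arm and the score's own T0 value, without genetic test result.
- The ST−UC difference will be reported with its 95% CI for each scale.
- Referrals made under the section 15.1 distress procedure will be counted by arm.
- MICRA will be described separately, stating who completed it.
- A non-significant difference will not be read as absence of harm; any statement on safety will quote the upper confidence limit.

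The cost is two extra regressions and a few sentences. The survey data are already planned, and no visits or participants are added.
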